10.8 Response in the Injected Lesions

Best response of CR, UCR, PR or UPR as specified in Section 10.3 taking into consideration only lesions deemed injectable at any time prior to progression as defined in Section 10.2d. All other disease must be stable or better. No new visceral or otherwise uninjectable lesions.

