1.1 Primary Objective(s)

To evaluate the objective response rate (confirmed complete and partial responses) of treatment with talimogene laherparepvec (T-VEC) in combination with pembrolizumab (MK-3475) following progression on prior anti-PD-1 or anti-PD-L1 therapy alone or in combination with other agents different from talimogene laherparepvec (T-VEC).

- 1.2 Secondary Objective(s)
 - a. To estimate the durable response rate (as defined in Section 10.7)
 - b. To estimate the objective response rate (ORR) defined as confirmed and unconfirmed, complete and partial responses in the injected lesions.
 - c. To estimate the ORR in the non-visceral, non-injected lesions.
 - d. To estimate the ORR in the visceral lesions (Cohort A).
 - e. To estimate the median progression-free survival (PFS).
 - f. To estimate the median overall survival (OS).
 - g. To evaluate the toxicity of the regimen.
- 1.3 Translational Objectives
 - a. To evaluate whether adding talimogene laherparepvec (T-VEC) to PD1 blockade can increase T-cell infiltration into tumors and whether change in T-cell infiltration is associated with response.
 - b. To evaluate whether adding talimogene laherparepvec (T-VEC) to PD1 blockade can increase TCR clonality in tumors and in peripheral blood and whether increased TCR clonality is associated with response.
 - c. To evaluate whether intra-tumoral injection of talimogene laherparepvec (T-VEC) can improve the tumor immune microenvironment.
 - d. To evaluate whether tumor mutational load, mutations in the IFN pathway, and circulating tumor DNA profile are associated with response to talimogene laherparepvec (T-VEC) plus pembrolizumab (MK-3475) therapy in the anti-PD1/L1 therapy refractory melanoma patients.

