2.2 Local and visceral ORR with talimogene laherparepvec (T-VEC) alone

The OPTiM trial included 3274 evaluable baseline and new lesions from 285 evaluable patients and 259 (91 %) of the 285 evaluable patients had three or more lesions (14).

a. Injected Lesions

Of a total of 2116 lesions injected with T-VEC from 277 patients, 1361 (64 %) lesions had a decrease in size of ≥50 % including 995 (47 %) lesions that resolved completely. Median time to response of responding injected lesions from baseline was 9.3 weeks. Among 277 patients evaluable for response in injected lesions, 37 % had ≥50 % decrease in total tumor area of injected lesions and 16 % had complete resolution of injected lesions. The ORR in these patients was 32 % (15 % CR).

b. Un-injected Non-Visceral Lesions

A total of 981 un-injected, non-visceral lesions (cutaneous, subcutaneous, or nodal) from 177 patients were evaluable, 331 (34 %) lesions decreased in size by \geq 50 %, and 212 (22 %) had CR. Among 177 patients evaluable for response, 21 % had \geq 50 % decrease in total tumor area of un-injected non-visceral lesions and 14 % CR, which corresponded to an ORR of 18 % and a CR rate of 6 %.

c. Visceral Lesions

Of a total of 177 individual visceral lesions from 79 patients, twenty-seven (15%) decreased in size by \geq 50%, and 16 (9%) CR. Evaluable visceral lesions were located in the lung (77%), liver (8%), adrenal gland (6%), spleen (3%), kidney (3%), pancreas (1%), and the thyroid, brain, and gastrointestinal tract (<1% each). Among responding visceral lesions, 81% were in the lung, 15% in the liver, and 4% in the thyroid. Among 79 patients evaluable for response in visceral lesions, 10% had a \geq 50% decrease in total tumor area of visceral lesions and 6% had complete resolution of visceral lesions. ORR was 14% and the CR rate was 3%.

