10.9 Response in visceral lesions

Best response of CR, UCR, PR or UPR as specified in Section 10.3 taking into consideration only visceral lesions present at baseline. All other disease must be stable or better. No new lesions.

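### The response rates for injected, visceral and non-injected lesions require all other disease to be at least stable, a condition objectives 1.2b–d do not contain, so a set's response first seen at or after progression elsewhere is scored as no response

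*Combined protocol and SAP*

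**What the plan says.** **Objectives.** Section 1.2b asks for an ORR "defined as confirmed and unconfirmed, complete and partial responses in the injected lesions". Section 1.2c reads "To estimate the ORR in the non-visceral, non-injected lesions", and section 1.2d reads "To estimate the ORR in the visceral lesions (Cohort A", followed by a closing bracket. None of the three mentions disease outside the set.

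**Endpoint definitions.** Section 10.8 scores the injected set "taking into consideration only lesions deemed injectable at any time prior to progression as defined in Section 10.2d", and then adds "All other disease must be stable or better. No new visceral or otherwise uninjectable lesions". Section 10.9 (visceral) adds "All other disease must be stable or better. No new lesions", and section 10.10 (non-injected) carries the same two conditions.

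**Analysis text.** Section 11.1c applies RECIST 1.1 with one set at a time as the target lesions. It does not repeat the condition on other disease. Section 11.2c only names the sets.

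**Related rules.** Under section 10.3, a single objective status of PR is enough for an unconfirmed PR, and unconfirmed responses count for these endpoints. Under section 10.2d, progression recorded at Week 9 or earlier must be confirmed at Week 13. Section 7.4b allows treatment to continue past RECIST progression, with repeat scans every 12 weeks.

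**The concern.** The objectives ask how often each lesion set responds. The definitions ask how often it responds while everything else is controlled. A patient whose injected lesions shrink while a liver lesion progresses at the same visit is a non-responder in the injected lesions.

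The protocol gives reasons to expect such patients. Its rationale (section 2.1) separates lysis of injected tumors from a systemic effect at uninjected sites. All entrants have already progressed on anti-PD-1 or anti-PD-L1 therapy. Section 3.2b reports that about half of eventual T-VEC responders first had growth of existing lesions or new lesions. Section 2.2a gives a median of 9.3 weeks to response in responding injected lesions, close to the Week 9 assessment, so local response and distant progression may first appear on the same scan.

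At stake is the reading of three named secondary objectives. A low scored rate could mean that the injected lesions did not shrink, or that they shrank while disease elsewhere grew. No planned table distinguishes these.

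**Working it through.** **Step 1. Which patterns are counted?** Taking the injected set in Cohort A and applying 10.8, 10.9, 10.3 and 10.2d:

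| Injected lesions | Visceral lesions | Scored under 10.8 |
|---|---|---|
| PR | stable | response (and no response under 10.9) |
| PR at one visit | progression at a later visit | response, as at least an unconfirmed PR |
| PR | progression by Week 9, absent at Week 13 | can count, because that progression is disregarded |
| PR first seen at the visit showing progression that stands | progression | **no response** |
| PR first seen later, treatment continued under 7.4b | progressed earlier | **no response** |

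Only the last two rows are lost. They are the patients with local response and progression elsewhere.

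**Step 2. Does section 11.1c remove the condition?** No. With one set as target, other disease becomes non-target. Under sections 10.2d and 10.2g, unequivocal progression of that disease, or a new lesion, is still progression. A change confined to 10.8–10.10 would leave this rule in place.

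**Step 3. Reproduce the plan's precision.** The half-width at p = 0.5 is 1.96 × √(0.25/n).

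- n = 17: 1.96 × √(0.25/17) = 23.77% (stated 23.7%)
- n = 25: 1.96 × √(0.25/25) = 19.6% (stated 19.6%)

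These depend on n alone, so the condition on other disease does not affect them.

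**Step 4. Effect on the scored rate.** Let L be the response rate judged on the set's own lesions, and q the share of those responders disqualified by disease elsewhere. The scored rate is L × (1 − q). Since q cannot be negative, the scored rate cannot exceed L.

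Inputs: L = 37%, borrowed as an illustration from section 2.2a, which reports it as follows: "Among 277 patients evaluable for response in injected lesions", 37% had at least a 50% decrease in tumor area. The documents do not give q, so a range is assumed.

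| q (assumed) | Scored rate | Fall | Expected responders of 17 |
|---|---|---|---|
| 0 | 37.0% | 0 | 6.3 |
| 10% | 33.3% | 3.7 points | 5.7 |
| 25% | 27.75% | 9.25 points (9.3 rounded) | 4.7 |
| 50% | 18.5% | 18.5 points | 3.1 |

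**Step 5. The scored rate does not identify L.** A scored 37% arises from L = 37% with q = 0, and equally from L = 50% with q = 26%, since 0.50 × 0.74 = 0.37.

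**Step 6. Scope.** Objective 1.2d applies to Cohort A only. Cohort B has no visceral lesions at entry, and 10.8 takes in every lesion deemed injectable, so little other disease may remain for the injected set there. In Cohort B the condition acts mainly through 10.10 and the bars on new lesions.

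**The case against.** The strongest reply is that the definitions are a coherent RECIST-style choice. A response normally requires no progression anywhere, and 11.1c follows the same logic by making one set the target and the rest non-target. That is a fair account of why the condition is there. It does not make the resulting quantity the one that objectives 1.2b–d name.

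A reader might go further and infer several things the documents do not support.

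- *That local and systemic effect cannot be separated, or that the three rates merely restate the overall ORR.* The first row of Step 1 shows otherwise: local response with stable visceral disease counts under 10.8 and not under 10.9.
- *That any distant progression cancels a local response.* A single PR before later progression is enough, and unconfirmed early progression is disregarded.
- *That the loss is large, say 13 to 20 points.* That follows from a 40% local rate with one third to one half disqualified (0.40 × 1/3 = 13 points; 0.40 × 1/2 = 20 points), but the documents give neither input. In section 2.2, the local figure and the ORR in the same patients are 37% and 32% (injected), 21% and 18% (un-injected non-visceral), and 10% and 14% (visceral). These are net gaps under a different criterion in a different population, so they neither bound nor support a large loss.
- *That the trial's rates will be tested against section 2.2.* Sections 11.1c and 11.2c plan estimation only. The 50% area criterion would also differ from a 30% diameter criterion.
- *That 10.8 contradicts itself* by tolerating new injectable lesions while referring to 10.2d, where any new lesion is progression. The reference can be read as saying which lesions enter the set, not as closing the response window. It is an ambiguity to settle.

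It also stands that these are secondary estimates with wide intervals.

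**Conclusion.** The concern holds in a limited form. Sections 10.8–10.10 attach a condition that objectives 1.2b–d do not state, and responses in a set first seen at or after progression elsewhere are neither counted nor shown. Each set's rate therefore mixes shrinkage in the set with control of other disease, and can only understate the set's own activity.

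The direction is certain. The size is not known: the illustrative falls of 3.7 to 18.5 points rest on a borrowed L and an assumed q of 10% to 50%. The primary ORR and the two-stage rules, with their error rates, are untouched. The change is worth making because the gap concerns named objectives and can be closed with data the trial already collects.

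**What to change.** 1. In 10.8–10.10, and in 11.1c and 11.2c, add a response rate for each set judged only on that set's own lesions. Use all on-treatment assessments, including those during treatment beyond progression. Drop both the condition on other disease and the bar on new lesions outside the set for this rate. State in 11.1c and 11.2c that progression outside the set does not override it.
2. Cross-tabulate this rate against the status of other disease, by cohort, with the visceral set for Cohort A only.
3. Keep the current conditional rate alongside it.
4. Align *deemed injectable* in 10.8 with *injected* in 1.2b and 11.1c. State whether new injectable lesions are allowed in the 10.8 response, given that 10.2d counts any new lesion as progression.

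The cost is definition wording and one table, with no change to sample size. The downside is that patients who leave treatment at distant progression are observed for less time in the set; the cross-table should show how many these are.

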10.9 Response in visceral lesions

Best response of CR, UCR, PR or UPR as specified in Section 10.3 taking into consideration only visceral lesions present at baseline. All other disease must be stable or better. No new lesions.

10.10 Response in non-injected (non-visceral) lesions

Best response of CR, UCR, PR or UPR as specified in Section 10.3 taking into consideration only lesions that were not injected at Cycle 1, Week 1. All other disease must be stable or better. No new lesions.

11.0 STATISTICAL CONSIDERATIONS

- 11.1 Cohort A: Patients who have injectable lesions and measurable visceral diseases
 - a. Cohort A will use a 2-stage design with an accrual goal of 17 eligible patients in total. This includes 9 eligible patients in the first stage and 8 eligible patients in the second stage. The anticipated accrual rate for Cohort A is 1 patient per month. Assuming an ineligibility rate of 10%, we will accrue 19 total patients (10 patients in the first stage and 9 patients in the second stage) to enroll 17 eligible patients.
 - b. Primary Endpoint: The primary endpoint for Cohort A is objective response (confirmed CR or PR) rate (ORR).

We propose a two-stage design with the assumption that a true ORR of 5% or lower indicates that the treatment will not be of further interest and that a true ORR of 25% or more would be of considerable interest. The alternative hypothesis of

25% ORR is what is felt to be a clinically significant antitumor activity of adding talimogene laherparepvec (T-VEC) to anti-PD-1 for a population of patients who are already progressing on prior anti-PD-1 therapy.

Initially, 9 eligible patients would be entered. If necessary, Cohort A may be temporarily closed to accrual while the data mature. If zero objective responses (confirmed PR/CR) are observed among these 9 patients, then Cohort A would be closed and the treatment determined to be inactive in this population. If one or more objective responses (confirmed PR/CR) are observed, then 8 more eligible patients would be accrued, for a total sample size of 17 eligible patients. Two or more objective responses (confirmed PR/CR) out of 17 patients would be considered evidence that the treatment warrants further study, provided other factors such as toxicity and overall survival also appear favorable. This design has an alpha of 17.2% (i.e. probability of declaring the regimen warrants further study when the true ORR is 5%) and a power of 90.2% (probability of declaring the regimen warrants further study when the true ORR is 25%).

c. Secondary Endpoints:

We will estimate the durable response rate. For Cohort A, with a total of 17 eligible patients, we will be able to estimate the durable response rate to within 23.7% (95% Cl).

We will estimate the response rate (complete and partial, confirmed and unconfirmed responses) by three different methods. RECIST 1.1 will be applied, but with the following restrictions: 1) considering only the injected lesions as target lesions, 2) considering only the non-injected lesions as target lesions,3) considering only the visceral lesions as target lesions and 4) across all lesions per RECIST guidelines. We will construct 95% confidence intervals for the estimated rates. For Cohort A, with a total of 17 eligible patients, assuming all 17 patients have both injected and non-injected measurable lesions, we will be able to estimate each of these response rates to within 23.7% (95% CI).

We will estimate the median PFS and median OS and construct 95% Brookmeyer-Crowley Confidence intervals. For Cohort A, with a total of 17 eligible patients, we will be able to estimate the PFS, OS, and DR rates at a particular time point (e.g., 6 months) to within 23.7% (95% CI).

To assess the association between objective response rate and CD8 T-cell infiltration in the injected tumors, we will use a two-sample t-test to test for difference in mean quantitative CD8 expression between patients who have an objective response and patients who do not have an objective response. We will control the type I error at the two-sided 0.05 level. For Cohort A, assuming 17 eligible patients and an ORR of 25%, then we anticipate 80% power to detect a mean difference in CD8 expression of 1.68 standard deviations. If the distributions are far from normal or subject to influential points, then instead of t-tests, we will use robust, rank based or non-parametric alternatives such as the Wilcoxon test. We will repeat the analysis to assess the association between durable response rate and CD8 T-cell infiltration in the non-injected tumors.

We will assess whether ctDNA fraction at baseline and Day 28 is associated with ORR using a two-sample t-test at the two-sided 0.05 level. For Cohort A, with 17 eligible patients and assuming 25% of patients have a response, we anticipate 80% power to detect a difference in mean ctDNA fraction of 1.68 standard deviations.

11.2 Cohort B: Patients who have injectable lesions and no visceral lesions

- a. Cohort B will use a 2-stage design with an accrual goal of 25 eligible patients in total. This includes 16 patients in the first stage and 9 patients in the second stage. Assuming an ineligibility rate of 10%, we will accrue 28 total patients to enroll 25 eligible patients.
- b. Primary Endpoint:

The primary endpoint for Cohort B is objective response (confirmed PR or CR) rate (ORR).

We propose a two-stage design with the assumption that a true ORR of 10% or lower indicates that the treatment will not be of further interest and that a true ORR of 30% or more would be of considerable interest. The alternative hypothesis of 30% ORR is what is felt to be a clinically significant antitumor activity of adding talimogene laherparepvec (T-VEC) to anti-PD-1 for a population of patients who are already progressing on prior anti-PD-1 therapy.

Initially, 16 patients would be entered. Cohort B may be temporarily closed to accrual while the data mature. If one or fewer objective responses (confirmed PR/CR) are observed among these 16 patients, then cohort B would be closed and the treatment determined to be inactive in this population. If two or more objective responses (confirmed PR/CR) are observed, then 9 more patients would be accrued, for a total sample size of 25 patients.

Five or more objective responses out of 25 eligible patients would be considered evidence that the treatment warrants further study, provided other factors such as toxicity and overall survival also appear favorable. This design has an alpha of 10% (i.e. probability of declaring the regimen warrants further study when the true ORR is 10%) and a power of 90% (probability of declaring the regimen warrants further study when the true ORR is 30%).

c. Secondary Objectives:

We will estimate the durable response rate. For Cohort B, with a total of 25 eligible patients, we will be able to estimate the durable response rate to within 19.6% (95% Cl).

We will estimate the ORR, in injected lesions, in non-injected lesions, across all lesions and construct 95% confidence intervals for the estimated rates. For Cohort B, with a total of 25 eligible patients, we will be able to estimate the ORR in injected lesions, in non-injected lesions, across all lesions to within 19.6%.

We will estimate the median PFS and median OS and construct 95% Brookmeyer-Crowley Confidence intervals. For Cohort B, with a total of 25 eligible patients, we will be able to estimate the PFS, OS, and DR rates at a particular time point to within 19.6% (95% CI).

To assess the association between objective response rate and CD8 T-cell infiltration in the injected tumors, we will use a two-sample t-test to test for difference in mean quantitative CD8 expression between patients who have a objective response and patients who do not have an objective response. We will control the type I error at the two-sided 0.05 level. For Cohort B, assuming 25 eligible patients and a ORR of 30%, then we anticipate 80% power to detect a mean difference in CD8 expression of 1.28 standard deviations. If the distributions are far from normal or subject to influential points, then instead of t-tests, we will use robust, rank based or non-parametric alternatives such as the Wilcoxon test.

We will repeat the analysis to assess the association between durable response rate and CD8 T-cell infiltration in the non-injected tumor.

We will assess whether ctDNA fraction at baseline and Day 28 is associated with ORR using a two-sample t-test at the two-sided 0.05 level. For Cohort B, with 25 eligible patients and assuming 30% of patients have a response, we anticipate 80% power to detect a difference in mean ctDNA fraction of 1.28 standard deviations.

11.3 Data and Safety Monitoring

There is no formal data and safety monitoring committee for single arm Phase II studies. Toxicity and accrual monitoring are done routinely by the Study Chair, study Statistician and the Disease Committee Chair. Endpoint monitoring is done by the study Statistician and Study Coordinator. Accrual reports are generated weekly and formal toxicity reports are generated every 6 months. In addition, the Statistical Center, Adverse Event Coordinator at the Operations Office, SAE Physician Reviewer, and Study Coordinator monitor toxicities on an ongoing basis.

12.0 DISCIPLINE REVIEW

Discipline review is not necessary for this study.

13.0 REGISTRATION GUIDELINES

13.1 Registration Timing

Patients must be registered prior to initiation of treatment (no more than 7 calendar days prior to planned start of treatment).

13.2 Investigator/Site Registration

For patient enrollment at participating sites: Local Institutional Biosafety Committee (IBC) approval is required before a site can enroll patients to T-VEC protocols.

Prior to the recruitment of a patient for this study, investigators must be registered members of a Cooperative Group. Each investigator must have an NCI investigator number and must maintain an "active" investigator registration status through the annual submission of a complete investigator registration packet to CTEP.

a. CTEP Investigator Registration Procedures

Food and Drug Administration (FDA) regulations and National Cancer Institute (NCI) policy require all investigators participating in any NCI-sponsored clinical trial to register and to renew their registration annually.

Registration requires the submission of:

- a completed *Statement of Investigator Form* (FDA Form 1572) with an original signature
- a current Curriculum Vitae (CV)
- a completed and signed *Supplemental Investigator Data Form* (IDF)
- a completed *Financial Disclosure Form* (FDF) with an original signature

Fillable PDF forms and additional information can be found on the CTEP website at http://ctep.cancer.gov/investigatorResources/investigator_registration.htm.

For questions, please contact the **CTEP Investigator Registration Help Desk** by email at [contact].

b. CTEP Associate Registration Procedures

The Cancer Therapy Evaluation Program (CTEP) Identity and Access Management (IAM) application is a web-based application intended for use by both Investigators (i.e., all physicians involved in the conduct of NCI-sponsored clinical trials) and Associates (i.e., all staff involved in the conduct of NCI-sponsored clinical trials).

Associates will use the CTEP-IAM application to register (both initial registration and annual re-registration) with CTEP and to obtain a user account.

Investigators will use the CTEP-IAM application to obtain a user account only. (See CTEP Investigator Registration Procedures above for information on registering with CTEP as an Investigator, which must be completed before a CTEP-IAM account can be requested.)

An active CTEP-IAM user account will be needed to access all CTEP and CTSU (Cancer Trials Support Unit) websites and applications, including the CTSU members' website.

Additional information can be found on the CTEP website at http://ctep.cancer.gov/branches/pmb/associate_registration.htm. For questions, please contact the **CTEP Associate Registration Help Desk** by email at [contact].

- c. CTSU Registration Procedures This study is supported by the NCI Cancer Trials Support Unit (CTSU).
 - 1. IRB Approval:

Each investigator or group of investigators at a clinical site must obtain IRB approval for this protocol and submit IRB approval and supporting documentation to the CTSU Regulatory Office before they can be approved to enroll patients. Assignment of site registration status in the CTSU Regulatory Support System (RSS) uses extensive data to make a determination of whether a site has fulfilled all regulatory criteria including but not limited to: an active Federal Wide Assurance (FWA) number, an active roster affiliation with the Lead Network or a participating organization, a valid IRB approval, and compliance with all protocol specific requirements.

Sites participating on the NCI CIRB initiative that are approved by the CIRB for this study are not required to submit IRB approval documentation to the CTSU Regulatory Office. For sites using the CIRB, IRB approval information is received from the CIRB and applied to the RSS in an automated process. Signatory Institutions must submit a Study Specific Worksheet for Local Context (SSW) to the CIRB via IRBManager to indicate their intent to open the study locally. The CIRB's approval of the SSW is then communicated to the CTSU Regulatory Office. In order for the SSW approval to be processed, the Signatory Institution must inform

the CTSU which CIRB-approved institutions aligned with the Signatory Institution are participating in the study.

2. Downloading Site Registration Documents:

Site registration forms may be downloaded from the S1607 protocol page located on the CTSU members' website.

- Go to https://www.ctsu.org and log in to the members' area using your CTEP-IAM username and password
- Click on the Protocols tab in the upper left of your screen
- Either enter the protocol # in the search field at the top of the protocol tree, or
- Click on the By Lead Organization folder to expand
- Click on the SWOG link to expand, then select trial protocol S1607
- Click on LPO Documents, select the Site Registration documents link, and download and complete the forms provided.
- 3. Requirements For **S1607** Site Registration:
 - CTSU Transmittal Sheet (optional)
 - IRB approval (For sites not participating via the NCI CIRB; local IRB documentation, an IRB-signed CTSU IRB Certification Form, Protocol of Human Subjects Assurance Identification/IRB Certification/Declaration of Exemption Form, or combination is accepted)

Special Protocol Specific Requirements (PSRs) for protocols utilizing T-VEC:

- For patient enrollment at protocol initiation: The Principle Investigator should submit a document confirming Approval from the local Institutional Biosafety Committee (IBC) at the initial site (PI's or the coordinating site)
- For patient enrollment at additional participating sites: Local IBC approval is required before members site can enroll patients to T-VEC protocols.
- Additional information can be found in protocol appendix Section 18.3.
- 4. Submitting Regulatory Documents:

Submit required forms and documents to the CTSU Regulatory Office, where they will be entered and tracked in the CTSU RSS.

ONLINE:	www.ctsu.org (members' section) → Regulatory Submission Portal		
EMAIL:	[contact] document submission only)	(for	regulatory
[contact]		
MAIL:	CTSU Regulatory Office [name]		

5. Checking Your Site's Registration Status:

You can verify your site registration status on the members' section of the CTSU website.

- Go to https://www.ctsu.org and log in to the members' area using your CTEP-IAM username and password
- Click on the Regulatory tab at the top of your screen
- Click on the Site Registration tab
- Enter your 5-character CTEP Institution Code and click on Go

Note: The status given only reflects compliance with IRB documentation and institutional compliance with protocol-specific requirements as outlined by the Lead Network. It does not reflect compliance with protocol requirements for individuals participating on the protocol or the enrolling investigator's status with the NCI or their affiliated networks.

